This stratified trial will follow two Simon's two-stage optimal designs(1), one for the untreated group, and one for the previously treated group. Each study (or otherwise stated, each stratum) has the same hypothesized design which will run in parallel. For the first stage, 9 patients will be accrued. If none of the 9 patients achieve a partial or complete response with ABT-888 plus 5FU and oxaliplatin, the combination will be rejected and the trial stopped. However, if at least 1 patient of the 9 (11%) achieves a partial or complete response in the first stage, then an additional 15 patients will be entered into the second stage, for a total of 24 patients in each stratum of these Phase II studies. If 3 (12%) or more patients achieve a partial or complete response, then the combination will be considered for further investigation among those patients. The sample sizes of 9 and 24 patients and the decision rules, in stages 1 and 2 respectively, are designed to differentiate a 5% ORR from a 25% ORR at a 1-sided 10% significance level and 90% power. Historically, the response rate of patients receiving single agent gemcitabine (previously considered the standard of care) is only about 8%.

[figure not shown]

Figure 1: Treatment schema

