5.6 Justification for the use of FOLFOX in Pancreatic Cancer

As described above, one standard option as first line therapy for patients with metastatic pancreatic cancer is single agent gemcitabine. Gemcitabine was approved after demonstrating a significant increase in overall survival over 5FU(19). However, in the last twelve years, dozens of clinical trials have been performed, attempting to improve efficacy over single agent gemcitabine. Remarkably, no clinically meaningful improvements have been obtained with regards to overall survival when gemcitabine was combined with a number of cytotoxic nor biological therapies (reviewed in(2)), and the overall survival consistently remains in the 6-7 month range for patients receiving first line therapy. Furthermore, the response rates for gemcitabine have been dismally low, and very consistently about 8%(2). Thus, the putative "standard" backbone of gemcitabine justifiably should be questioned and reconsidered.

The combination of 5FU and oxaliplatin (typically a FOLFOX iteration) as a therapeutic option for patients with metastatic pancreatic cancer has been promising. Numerous phase II trials have demonstrated intriguing overall survival rates in the first, and even the second line setting for patients with metastatic pancreatic cancer. For example, Ducreux, *et al*, demonstrated a response rate of 10% with an overall survival rate of 9 months in previously untreated patients with metastatic pancreatic cancer treated with 5FU + oxaliplatin(5). In another first-line trial, Ghoshn, *et al*, demonstrated a response rate of 27%, with a median overall survival of 7.5 months(6). Second line trials have demonstrated response rates of 2.5 to 23% and overall survival rates (as second line therapy) of 4 to 6 months(7, 20, 21).

Recently, the most promising data came from the results of the CONKO-003 trial. Patients who had progressed on gemcitabine were randomized to 5FU + oxaliplatin vs. 5FU alone. Patients treated with a combination of 5FU and oxaliplatin had a median overall survival of ~11 months as measured from the start of gemcitabine therapy, which is the longest seen in a Phase III trial(3). Surprisingly, a Phase III comparison of FOLFOX and gemcitabine has never been attempted.

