13.3 Sample Size Considerations

For phase I, the sample size will range from 3 to 48 (estimate =24) depending on DLTs experienced. For each stratum of the phase II portion, the sample sizes of 9 and 24 patients and the decision rules, in stages 1 and 2 respectively, are designed to differentiate a 25% ORR from a 5% ORR. The ORR associated with single agent gemcitabine (the standard of care in pancreatic cancer) is only 8% across multiple large Phase III trials. The ORR of the combination of 5FU and oxaliplatin in the first or second-line setting ranges from 2.5 to 23% in Phase II studies. Thus the lower efficacy limit of 5% is essentially that of gemcitabine, and would suggest the combination is no more effective than single agent gemcitabine, and further investigation would not be warranted. The upper efficacy limit of 25% would be the highest observed to date in a Phase II study of 5FU and oxaliplatin in pancreatic cancer, and would be highly suggestive of a significant benefit to the addition of ABT-888 to the regimen and there would be sufficient evidence to warrant further investigation of this combination. The probability of erroneously concluding that the treatment regimen merits further investigation is 10% ($\alpha=0.10$) when the true ORR is less than 5%. Similarly, the probability of erroneously concluding that the treatment has an ORR of 5% (p_0) or less when the true ORR is 25% (p_1) is 10% (β); therefore the overall power of the study is 90%. The decision rule for this Simon design will accept this agent for further investigation if the sample ORR is 12% or greater at the end of stage 2.

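### Section 13.3 misdescribes what the 5% and 25% response rates stand for: the protocol's own figures are 8% for gemcitabine and up to 27% for 5FU plus oxaliplatin without ABT-888

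*Combined protocol and SAP*

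**What the plan says.** Each stratum (untreated, previously treated) uses the same Simon two-stage design: 9 patients, stop if there is no response; otherwise 15 more, and a go if at least 3 of 24 respond (13.2). Section 13.3 sets the null at 5%, the target at 25%, alpha at 10% and power at 90%, and ties alpha to the case "when the true ORR is less than 5"%.

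It then explains the two rates:

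- Gemcitabine: "The ORR associated with single agent gemcitabine (the standard of care in pancreatic cancer) is only 8% across multiple large Phase III trials". Two sentences later: "Thus the lower efficacy limit of 5% is essentially that of gemcitabine".
- 5FU plus oxaliplatin: the response rate "in the first or second-line setting ranges from 2.5 to 23% in Phase II studies".
- Target: "The upper efficacy limit of 25% would be the highest observed to date in a Phase II study of 5FU and oxaliplatin", and a rate of that size "would be highly suggestive of a significant benefit to the addition of ABT-888".

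Elsewhere, the synopsis (2.5) says "Historically, the response rate of patients receiving single agent gemcitabine (previously considered the standard of care) is only about 8"%, and section 5.6 says "the response rates for gemcitabine have been dismally low, and very consistently about 8"%. Section 5.6 also reports two first-line trials of 5FU plus oxaliplatin, with response rates of 10% and 27%, and gives 2.5 to 23% as the range for second-line trials.

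**The concern.** Section 13.3 is where a reader learns what passing or failing the trial would mean. Four of its statements do not fit the protocol's own figures:

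1. The null of 5% is presented as the gemcitabine rate, which the protocol gives as 8% in three places.
2. The range 2.5 to 23% is labelled first- or second-line. Section 5.6 gives it for second-line only, so the merged label leaves out the first-line 27%.
3. The target of 25% is called the highest seen with this backbone in a Phase II study in pancreatic cancer. Section 5.6 reports 27%.
4. A rate of 25% is taken as strong evidence that ABT-888 adds benefit, although backbone rates near or above 25% are cited without it.

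At stake is interpretation. The 10% error attached to 5% could be carried over to the gemcitabine rate, and a response rate of about 25% could be credited to ABT-888 on the authority of the sample-size section. The gemcitabine point bears mainly on the untreated stratum: section 14.4 names gemcitabine as standard for untreated patients and says there is no standard for previously treated ones, and 5% lies inside the cited second-line range.

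**Working it through.** **Inputs.** Stage sizes 9 and 15 and the cut-offs 1/9 and 3/24 come from 13.2; 5% and 25% from 13.3; 8% from 13.3, 5.6 and the synopsis; 10%, 27% and 2.5 to 23% from 5.6.

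**Formula.** With X1 ~ Bin(9, p) and X2 ~ Bin(15, p), the probability of passing stage 1 and reaching a total of at least k is

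P(k; p) = Σ over x = 1..9 of P(X1 = x) · P(X2 ≥ k − x).

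For the go rule, k = 3, this becomes

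P(go) = P(X1 = 1)·P(X2 ≥ 2) + P(X1 = 2)·P(X2 ≥ 1) + P(X1 ≥ 3).

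**The plan's own figures.**

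- p = 5%: 0.2985 × 0.1710 + 0.0629 × 0.5367 + 0.0084 = 0.093. Alpha of 10% is met.
- p = 25%: 0.2253 × 0.9198 + 0.3003 × 0.9866 + 0.3993 = 0.903. Power of 90% is met.
- An exhaustive search for 5% against 25% with both errors at most 10% returns 0/9 then 2/24 as the optimal design, which is exactly the stated one.

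**At the protocol's other rates.** For p = 8%: 0.3695 × 0.3403 + 0.1285 × 0.7137 + 0.0298 = 0.247.

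| True ORR | What the protocol cites it as | P(go), ≥3/24 | P(≥6/24) |
|---|---|---|---|
| 5% | null | 9.3% | 0.1% |
| 8% | gemcitabine | 24.7% | 1.0% |
| 10% | first-line backbone, lower | 36.4% | 2.7% |
| 23% | second-line backbone, top | 87.1% | 47.6% |
| 25% | target | 90.3% | 56.7% |
| 27% | first-line backbone, higher | 92.7% | 65.1% |

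At 2.5%, the bottom of the second-line range, P(go) is 1.7%.

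**What each total excludes.** Solving P(k; p) = 0.10 for p gives the one-sided 90% lower limit: 3/24 → 5.2%, 4/24 → 7.8%, 5/24 → 10.7%, 6/24 → 13.8%. So the go rule holds error at 10% up to a true rate of about 5.2%. A minimal go (3/24), or 4/24, does not exclude 8%; 5/24 is the smallest total that does, and it also excludes 10%.

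**The ABT-888 statement.** An observed 25% is 6/24. In the untreated stratum, 6 or more responses is improbable at a backbone rate of 10% (2.7%) but more likely than not at 27% (65.1%). In the previously treated stratum it is close to an even chance at 23% (47.6%). All three are cited rates without ABT-888. Read as a true rate, 25% lies between the two first-line figures and only 2 points above the top of the second-line range.

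**The case against.** **The design is valid and 13.3 ties alpha to 5%.** This stands in full. A reader might infer from the 24.7% that the trial's type I error is wrong. It is not: error held near the null and rising above it is how any such rule behaves. Only the label on the null is at fault.

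**The protocol never claims that a go beats gemcitabine.** This also stands. A go leads only to further investigation (2.5, 13.2, 13.3), and the ABT-888 remark is attached to a rate of 25%, not to 3/24. Superiority to gemcitabine is at most something a reader could draw from the 5% label. Nor would it be right to say that no go could exclude gemcitabine's rate, since 5/24 or more does.

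**The 27% study is an imperfect benchmark.** By its title in the reference list it includes locally advanced disease, and against the 10% trial an observed 25% would be unusual. That limits how much weight 27% can bear. It does not rescue the claim that 25% is the highest observed, because 13.3 speaks of pancreatic cancer without restricting to metastatic disease. The second-line 23% gives the same difficulty without using that study.

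**The historical rates may not transfer.** Phase II is restricted to patients with a BRCA-associated mutation or a suggestive family history (8.2), and the documents do not show that the cited rates come from such patients. This stands: the probabilities at 8%, 10%, 23% and 27% are illustrative. It also weakens further any attribution of a 25% rate to ABT-888.

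**Conclusion.** The concern holds as a minor correction to the stated rationale. On the protocol's own figures, 5% is not the gemcitabine rate, 2.5 to 23% is not a first-line range, 25% is not the highest backbone rate, and a response rate of 25% does not by itself indicate an ABT-888 effect in either stratum. At 8% the probability of a go is 24.7%, against the 9.3% attained at 5%.

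The figures rest on exact binomial calculation with the stated rule and on taking the cited historical rates at face value. The documents do not support reading 24.7% as this trial's actual false-positive rate, because the true rate on standard treatment in the selected Phase II population is not given. Nor do they support calling the design, decision rule or analysis faulty.

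**What to change.** Change wording in 13.3 only.

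1. Replace the sentence equating 5% with gemcitabine by: *The lower limit of 5% is below the cited gemcitabine rate of 8%. If the true ORR is 8%, the probability of meeting the go rule is 24.7%. The cited historical rates are not shown to come from BRCA or family-history selected patients, so this figure is illustrative.* The caveat should stay beside the figure. If a reason for keeping 5% is added, it should be dated and marked as written after Phase II began, because section 9.4.3.3.1 already refers to outcomes in Phase II patients.
2. Give the backbone rates by line: first-line 10% and 27% (noting that the 27% study includes locally advanced disease by its title), second-line 2.5 to 23%. Delete the statement that 25% is the highest observed.
3. Delete the clause crediting ABT-888 and keep the clause that 25% would warrant further investigation. Add: *Meeting the go rule rejects an ORR of 5% or less at the one-sided 10% level. It does not by itself show superiority to gemcitabine or a contribution of ABT-888.*

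A short table of go probabilities by stratum is optional.

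Cost: a few sentences, with no extra patients and no change to sample size, decision rule or analysis. The downside is that a less favourable go probability at the gemcitabine rate becomes visible and the sentence supporting ABT-888 is lost.

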13.4 Endpoints

13.4.1 Primary Endpoint: Objective response rate

Response classification will follow the RECIST criteria and will be defined as partial response (PR) or complete response (CR) as described in section 10. Patients who are lost to follow-up without a valid response assessment will be classified as non-responders.

13.4.2 Secondary Endpoints

13.4.2.1 Disease Control Rate

Disease control response classification will follow the RECIST criteria and will be defined as successful confirmed classification of stable disease (SD), partial response (PR), or complete response (CR) as described in section 10. Patients who are lost to follow-up without a valid response assessment will be classified as non-responders

13.4.2.2 Progression Free Survival

Progression-free survival will be defined as the time in days from study entry until progression or death. Patients who are alive and free from progression on the date of closing follow-up will be censored on that date.

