Study activities are presented in Table 3, and an early study activities checklist through cycle 2 is detailed in Table 4. Screening will occur within 14 days, prior to administration of the first dose of ABT-888 on Day 1 (baseline imaging scans must be done within 28 days of Day 1). All patients with biopsy-able tumor deposits will undergo the pre-treatment tumor biopsy prior to cycle 1, Day 1. During cycles 1 and 2, subject assessments (physical examinations including neurologic assessment, vital signs, performance status, medication review, chemistry, hematology and adverse event evaluations) will be conducted on Day 1 of each cycle. Beginning at cycle 3, patients will be seen on Day 1 of every other cycle (i.e. C3, D1; C5, D1; C7, D1, etc). Study procedures may be performed 2 days before or after the scheduled visit date, due to unforeseen or unavoidable circumstances. The neuropathy quality of Life assessment will occur during treatment for each odd-numbered treatment. Restaging studies will be performed every 4 cycles (or not more than every 12 weeks if there have been treatment delays). Patients who are adequately tolerating therapy, and whose restaging studies reveal no evidence of disease progression, by RECIST 1.1 criteria, will continue on study for an additional 4 cycles.

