The primary endpoint of the Phase I portion is the determination of the recommended Phase II dose. The primary endpoint of the Phase II portion will be the objective response rate (ORR), as determined by RECIST 1.1 criteria. Secondary clinical endpoints are determination of the disease control rate (DCR, defined as ORR + rate of stable disease at 6 months), progression free survival (PFS), overall survival (OS), time to disease progression (TTP), duration of disease control (DDC), tolerability and safety of the combination, and degree of neuropathy, as measured by the FACT/GOG-NTX-4 (Version 4). Patients whose tumors have not progressed at the time of restaging, as determined by RECIST 1.1 criteria, and who continue to tolerate treatment will continue treatment for an additional eight weeks. When an investigator has determined that a subject should discontinue the study, a Final Visit will be conducted. Information pertaining to survival and post treatment therapy will be collected approximately every 12 weeks (Month 3, 6, 9, 12, 15 and 18) beginning after the final visit, for a period up to 24 months. Tumor biopsy procedures for the pilot subgroup are discussed in detail in section 12.

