8.3 Efficacy and Safety Assessments/Variables

8.3.1 Efficacy and Safety Measurements Assessed and Flow Chart

Study procedures for safety and exploratory efficacy assessments will be performed as summarized in Table 3, and a checklist of study activities through cycle 2 is detailed in Table 4.

Table 3: Study Activities

	Screening	Cycle 1 and Cycle 2, Day 1 ^{aaa}	Day 3 of Each Cycle	Day 1 of every odd numbered cycle (Beginning cycle 3)	Day 1 of every even numbered cycle (Beginning cycle 4)	After every 4 cycles	Off Study	Final Follow-up Visit	Every 3 months
Informed consent	X								
Demographics	X								
Medical history	X								
Concurrent meds	X	X		X			X	X	
β-HCG	X ^{bbb}	X ^{bbb}							
Dispense Medications		X		X	X				
Disconnect 5-FU			X						
Physical exam	X	X		X			X	X	
Vital signs	X	X	X	X	X		X	X	
Height	X								
Weight	X	X		X	X		X	X	
Performance Status	X	X		X			X	X	
CBC w/diff	X	X		X	X		X	X	
Serum chemistry ^{ccc}	X	X		X	X		X	X	
PT/PTT/INR	X								
Adverse event evaluation	X	X		X			X	X	
Neuropathy QOL Assessment	X			X					
PK Sampling	See Table 5 for Details								
Radiologic evaluation and Tumor Measurements	X ^{ddd}					X ^{fff}	X ^{ggg}		
Tumor Biopsy	X						X		
Research Serum Sample	X					X	X		
Progression and Survival						X		X	X

^{aaa}For the phase I portion, if any patient has been escalated from one dose cohort to another (up or down) then that particular patient will be on Day 1 of the first two cycles of the new dose level as well.

^{bbb}Urine or Serum pregnancy test (women of childbearing potential) at screening and Cycle 1, Day 1 ONLY

^{ccc}Albumin, alkaline phos, total bili, bicarbonate, BUN, calcium, chloride, creatinine, glucose, potassium, total protein, AST, ALT, sodium.

^{ddd}Screening scans should have been within 4 weeks of starting treatment.

^{eee}Optional serial samples

^{fff}But not more than every 12 weeks, if there have been treatment delays

^{ggg}If not done within the previous 4 weeks

Table 4: Early Study Activities Checklist**Screening/Pre-Treatment**

Subject Assessment	_____
Eligibility Criteria	_____
Informed Consent	_____
Pregnancy Test (if appropriate)	_____
Radiology within 4 weeks	_____
Blood for research	_____
PT/PTT/INR	_____
Tumor biopsy	_____

Cycle 1, Day 1

Subject Assessment	_____
Pregnancy Test (if appropriate)	_____
5FU, oxaliplatin, and ABT-888 Dosing	_____
ABT-888 Pharmacogenomics	_____

ABT-888 PKs (0, .5, 1, 2, 4, and 6 hours) _____

Vital Signs	_____
5-Fluorouracil disconnect	_____

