13.4.2.3 Overall Survival

Overall survival will be defined as the time in days from study entry until death. Patients who are alive on the date of closing follow-up will be censored on that date. All events of death will be included, regardless of whether the event occurred while the subject was still taking study drug, or after the subject discontinued study drug. If a subject has not died, then the data will be censored according to the following rule: if the subject was lost to follow-up, then data will be censored at the last study visit, or the last contact date, or the date the subject was last known to be alive, whichever is later; if the subject was not lost to follow-up, then data will be censored at the last study visit or the last contact date, whichever is later. The date of the last study visit will be determined by selecting the last available date of the following study procedures for a subject: tumor assessment, physical examination including neurologic assessment, vital signs assessment, blood chemistry and hematology collection, and performance status.

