13.4.2.5 Duration of Disease Control

The duration of disease control for a given subject is defined as the number of days from the date the criteria are met for CR, PR, or SD (whichever is recorded first) to the date that recurrence or PD is objectively documented. The reference for PD will be the smallest measurements recorded since the treatment started. If a subject is still responding then the subject's data will be censored at the date of the subject's last study dose or last available tumor assessment, whichever is later. For subjects who never experienced CR, PR, or SD for 6 months, the subject's data will be censored on the date initiation of therapy.

13.4.2.6 Statistical survival analyses of marker levels to determine impact on prognosis and response to treatment

The relative risk for disease progression will be estimated using the Cox proportional hazards regression model. The Cox model will be used for both univariate and multivariate analyses provided the assumption of proportional hazards is verified. The Xtiles software(31, 32) will be employed to determine cut-points for the quantitative signals for analyzed biomarkers in association with survival and response to treatment as primary outcome. This software has built-in features for dividing the cohort into training and validation subsets, with correct assessments of p values for multiple cut-points. In the multivariate analyses of biomarkers, the Cox regression models will be adjusted for tumor size (continuous variable, 1 mm units), tumor grade (well, moderately, poorly differentiated), tumor stage (T1, T2, T3), lymph node metastasis (N0, N1). Univariable models will be run, with covariates having $p < 0.2$ included in backwards stepwise multivariable models. Final covariates will be retained with $p \leq 0.05$ based on two-sided tests. Limited interactions may be explored based on the final main effects model to avoid over-fitting of the models with this small sample size.

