13.5.1.2.2 Progression Free Survival

The progression-free survival estimate curves will be calculated and presented by the methods of Kaplan and Meier (1958) and 95% confidence interval will be constructed for the estimated 12-month progression-free survival rate and for the median.

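### PFS is censored when follow-up closes, not at the last tumour assessment, which raises 12-month PFS to the extent that later progression goes unascertained

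*Combined protocol and SAP*

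**What the plan says.** Section 13.4.2.2 defines the endpoint: "Progression-free survival will be defined as the time in days from study entry until progression or death". Its only censoring rule is "Patients who are alive and free from progression on the date of closing follow-up will be censored on that date". It does not mention the last scan, withdrawal, loss to follow-up or new therapy, and no other section supplies such a rule for PFS. Section 13.5.1.2.2 then commits to Kaplan-Meier estimates in which a "95% confidence interval will be constructed for the estimated 12-month progression-free survival rate and for the median".

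The neighbouring endpoints are treated differently:
- **Overall survival** (13.4.2.3) starts from the same closing-date sentence but adds a rule for lost patients: "if the subject was lost to follow-up, then data will be censored at the last study visit, or the last contact date", or the date last known alive if later.
- **Duration of disease control** (13.4.2.5) censors at the "last study dose or last available tumor assessment, whichever is later".
- **Time to progression** (13.4.2.4) uses the closing date, as PFS does.

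On scanning, Section 8.1 says: "Restaging studies will be performed every 4 cycles (or not more than every 12 weeks if there have been treatment delays"). In Table 3 the row "Radiologic evaluation and Tumor Measurements" is marked at screening, after every 4 cycles and off study. It is not marked at the final follow-up visit or every 3 months. A separate progression-and-survival row is marked every 3 months, with no method of assessment given. Section 8.1 describes the follow-up contact more narrowly: "Information pertaining to survival and post treatment therapy will be collected approximately every 12 weeks".

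**The concern.** PFS can only be called event-free for as long as someone is looking for the event. Section 8.5 lets patients leave for reasons other than progression, such as withdrawn consent or investigator judgement. Section 13.5.4 then follows survival for up to 24 months after discontinuation. The closing date can therefore fall many months after a leaver's last scan. If that patient's progression is not picked up some other way, the whole interval counts as progression-free time.

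What is at stake is a reported 12-month rate with its confidence interval, in a single-arm trial where no concurrent control shares the bias. With 24 patients per stratum, 10% leaving is two or three people (24 × 0.10 = 2.4).

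**Working it through.** **Plan's own figures.** The documents give no expected PFS, event count or drop-out rate, so there is no PFS figure to reproduce. The only efficacy calculation is the Simon design for response rate (0/9, then at least 3/24). Exact binomial calculation gives a type I error of 0.093 at 5% and power of 0.903 at 25%, in line with the stated 10% and 90%. PFS plays no part in it.

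**Inputs from the documents.** Scans every 4 cycles of 14 days = 8 weeks; 24 patients per stratum; accrual 24 to 30 months (30 used); minimum follow-up 8 weeks.

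**Assumptions.** Exponential PFS with median *m*; a fraction *w* leaves scanning before progression, unrelated to prognosis; median survival after progression 5 months; closing at month 36.

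**Hand check: nothing captured after leaving, leavers carried to closing.** With constant hazards and closing after month 12:

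- recorded events by 12 months = (1 − w) × [1 − 2^(−12 / (m(1 − w)))]
- PFS as written = 1 − that figure; true PFS = 2^(−12/m)

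For m = 6 the true value is 2^(−2) = 25.0%.
- w = 0.1: 1 − 0.9 × (1 − 0.214) = 29.3%, excess 4.3 points
- w = 0.2: 1 − 0.8 × (1 − 0.177) = 34.1%, excess 9.1 points
- w = 0.3: 1 − 0.7 × (1 − 0.138) = 39.7%, excess 14.7 points

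**Simulation** (1,200 trials of 24 patients per scenario). Mean 12-month PFS in %, rule as written v censoring at the last scan:

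| Median (months) | Leaving | Nothing captured later | Deaths only | Progression found every 3 months |
|---|---|---|---|---|
| 4 | 10% | 20.5 v 14.2 (+6.3) | 17.1 v 14.1 (+3.0) | 15.2 v 14.6 (+0.6) |
| 4 | 20% | 26.9 v 13.6 (+13.3) | 20.5 v 13.7 (+6.8) | 14.6 v 13.1 (+1.5) |
| 4 | 30% | 34.6 v 13.3 (+21.3) | 23.5 v 13.1 (+10.4) | 15.8 v 13.4 (+2.4) |
| 6 | 10% | 31.9 v 27.4 (+4.5) | 29.5 v 27.2 (+2.3) | 28.0 v 27.5 (+0.5) |
| 6 | 20% | 36.1 v 26.6 (+9.5) | 31.3 v 26.3 (+5.0) | 28.6 v 27.2 (+1.4) |
| 6 | 30% | 41.3 v 26.2 (+15.1) | 34.2 v 26.1 (+8.1) | 28.0 v 25.5 (+2.5) |

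The first column agrees with the hand check (+4.5, +9.5, +15.1 against +4.3, +9.1, +14.7). Three further results:
- **No leavers:** no difference (27.5 v 27.4 at a 6-month median). The 8-week gap before closing is not the problem; patients who stop being scanned are.
- **Last-scan censoring** is close to neutral. Across the grid it sits at most 1.7 points below the result with everyone scanned throughout (25.5 v 27.2).
- **Median PFS:** at 4 to 6 months with 10 to 20% leaving, the two rules differ by at most 0.2 months (5.5 v 5.3). The largest gap is at an assumed 9-month median with 30% leaving and nothing captured (12.9 v 9.2).

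A separate simulation over medians of 4 to 6 months with 7 to 23% leaving gave about +3 to +9 points with deaths only, +6 to +17 with nothing captured, and +1 to +3 with progression ascertained every 3 months. A variant gave 2 to 6 and 5 to 16 for the first two. These are orders of magnitude, not forecasts.

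**The case against.** The strongest reply has four parts.

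1. **The rule covers only patients who are alive and progression-free at closing.** A lost patient is not known to be either. The overall survival section opens with the same sentence and then adds a separate rule for lost patients, so the sentence was probably not meant for them. This stands. A reader might infer that the plan orders lost patients to be carried to closing; it does not say so, and the largest figures describe that implementation only. But on this narrow reading, leavers of unknown status have no PFS censoring rule at all, which is also a gap.
2. **Imaging is not the only way to record progression.** Section 10.2.5 counts clinical progression, including a need for palliative radiation, chemotherapy or surgery. The 12-weekly contact collects later therapy, and Table 3 has a three-monthly progression row. If these work, the excess is about 1 to 3 points. This stands as a condition. It is not secured, because Section 8.1 does not name progression among the items collected and no method is given.
3. **Censoring everyone at new anti-cancer therapy would do harm.** It would turn events under Section 10.2.5 into informative censoring. Under an assumed 5-month median, with 10, 20 or 30% of events being of this kind, 12-month PFS rises from 19.0% to 22.1, 25.7 or 29.9%. This stands, and the fix avoids it.
4. **The shift is modest beside sampling error.** With 24 patients, the 95% half-width at a rate of 20 to 25% is 1.96 × √(0.20 × 0.80 / 24) = 16 points to 1.96 × √(0.25 × 0.75 / 24) = 17 points. True, but the interval does not allow for a systematic shift.

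**Conclusion.** The concern holds in conditional form. The closing-date rule keeps unscanned leavers at risk as progression-free. Where their later progression is not ascertained, the systematic effect on 12-month PFS is upward compared with full ascertainment.

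Assuming a median of 4 to 6 months and 7 to 23% leaving, the excess is about 3 to 9 points if only deaths are captured, larger if lost patients are carried to closing, and about 1 to 3 points if progression is ascertained every 3 months. If nobody leaves scanning early, it is nil. The median, drop-out and survival after progression are all assumptions.

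Two stronger readings are not supported. A reader might infer that reported PFS will be inflated whatever happens; that depends on how many leave and what the three-monthly contact collects. A reader might also infer that PFS will be set against historical values; the plan specifies only estimates with confidence intervals, and its historical benchmarks are response rates and overall survival.

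PFS is secondary and the go/no-go decision rests on response rate, so that decision is unaffected. The wording should still be settled before analysis.

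**What to change.** - **Rewrite 13.4.2.2.** Patients without documented progression (radiologic, or clinical as defined in 10.2.5) or death are censored at the last tumour assessment showing no progression, or at study entry if there is none after baseline. This also covers withdrawal and loss to follow-up.
- **Use the same censoring date for time to progression** (13.4.2.4).
- **Keep new palliative therapies that meet 10.2.5 as events.** Do not adopt blanket censoring at new anti-cancer therapy.
- **Keep closing-date censoring as a sensitivity analysis.**
- **Reconcile Section 8.1 with Table 3** on whether the three-monthly contact collects progression, and if so how it is established.

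The cost is a few sentences and a little programming, with no change to sample size. The downside is a slightly less favourable PFS figure.
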